6.2.6 Change in Background Antiretroviral Regimen

- a. Subjects who change their background treatment regimen before week 4 will be discontinued from the study. Those subjects that change their background treatment regimen after week 4 and who choose to continue MVC treatment intensification will be followed on the study.
- b. If the regimen change is due to toxicity, then the subject would be followed per criteria of a Change of Therapy Due to Toxicity visit (section 6.1).

6.2.7 Virologic Failure during the MVC treatment intensification portion of study

Virologic failure will be decided on a case by case basis by the local site's study investigator in collaboration with the protocol team. Suggested criteria include: two consecutive HIV RNA loads > 50 copies/mL. For subjects who develop a plasma HIV-1 RNA > 50 copies/mL, a confirmatory plasma HIV-1 RNA test must be performed within 4 weeks of the initial HIV-1 RNA sample. Subjects who meet criteria for confirmed virologic failure will undergo real-time genotypic resistance and tropism testing (testing not provided by study) and alternative regimen will be chosen by the site investigator with recommendations of the protocol team. Follow-up intervals will continue per study protocol, but the site investigator may schedule additional non-study, safety visits as necessary. The patient will be followed off study medication but on study for the remainder of the study.

6.2.8 Post-Treatment Evaluations

All randomized subjects who complete the 24 weeks of MVC intensification will complete the week 36 post-MVC intensification visit.

6.2.9 Pregnancy

Women who become pregnant during the study will be required to permanently discontinue their MVC treatment intensification. They should be advised to seek best available medical care for their pregnancy according to USPH Guidelines

6.3 Special Instructions and Definitions of Evaluations

6.3.1 Documentation of HIV

HIV-1 infection documented by a rapid HIV test or any licensed ELISA test kit and confirmed by a different method ELISA, Western blot, rapid HIV test, or plasma HIV-1 RNA assay at any time prior to study entry. Alternatively, if a licensed ELISA is not available, two HIV-1 RNA values >2000 copies/mL at least 24 hours apart by any CLIA certified laboratory may be used to document HIV-1 infection at any time prior to study entry.

6.3.2 Medical and Laboratory History

At screening a medical history will be obtained and must be recorded in the source documents. The medical history should include any previous HIV-related diagnoses and AIDS-defining events.

In addition, prior to obtaining screening laboratories, documentation of all historic plasma HIV-1 RNA load and CD4+ T-cell counts since initiation of first ARV regimen must be recorded in the source documents and on-line CRF form (www.cfar.ucsd.edu/intranet). **Of note:** a minimum of 3 CD4+ T-cell (below 350 cells/mm³) and HIV RNA values (below 50 copies/mL) obtained \geq 30 days apart must be obtained and recorded.

6.3.3 Medication History

At screening, a complete history or all prior antiretroviral medications will be recorded in the CRF. For all other medications, a medication history (**only of those taken within the last 30 days prior to entry**) with actual or estimated start and stop dates should be obtained and recorded in the source documents and the concomitant medication CRF, including:

- All prescription medications. Including medications taken for the treatment or prophylaxis of opportunistic infections.
- Non-prescription medications.
- Alternative therapies and/or dietary supplements.
- Allergies to any medications and their formulations must be documented.

6.3.4 Concomitant Medications

During study visits (See section 6.1 for specific dates) all concomitant medications taken since the last visit will be recorded in the source documentation and entered into the concomitant medication log CRF.

6.3.5 Study Treatment Modifications

All modifications to study drug(s) including initial doses, patient-initiated and/or protocol-mandated interruptions, modifications, and permanent discontinuation of HIV antiretrovirals need be recorded on the CRFs at each visit. The same needs to be done for all background antiretroviral agents.

6.3.6 Clinical Assessments

Complete Physical Exam

A complete physical examination will be performed at entry. Documentation must include a complete review of systems and any HIV-related, toxicity-related, or AIDS-defining events.

Targeted Physical Exam

A targeted physical examination will be based on any signs or symptoms previously identified that the subject has experienced within 30 days of entry or since the last visit. This examination will be performed at entry, weeks 12, 24 and 36 and in instances of virologic failure or premature treatment discontinuation if they should occur. Documentation must include any HIV-related, toxicity-related, or AIDS-defining events.

Height and Weight

Height and weight should be measured at study entry.

Signs and Symptoms

All signs, symptoms, deaths, and toxicities must be documented in the subject's record. At entry, record all signs/symptoms experienced within 30 days of entry on the CRFs. For all other visits including the time of confirmation of virologic failure, record all Grade ≥ 2 signs and symptoms, HIV-related and AIDS-defining events and deaths on the CRFs that have occurred since the last visit. Any signs or symptoms that lead to a change in treatment, regardless of Grade, must be recorded on the CRF. The source document must include date of onset and date of resolution, but the CRF will only record prevalence of a given adverse event since the previous study visit.

Refer to the Division of AIDS Table for Grading Adult Adverse Experiences, which can be found on the CCTG website: www.cctg.ucsd.edu

Diagnoses

The following should be recorded on the CRFs: HIV-related diagnoses, HIV-related malignancies, non-HIV related malignancies, myocardial infarctions,

hepatic failures, AIDS-defining events and death. Any other diagnosis that is, in the opinion of the site investigator, associated with study medications, should be recorded on the adverse event CRF. The source document must include date of diagnosis and date of resolution.

Karnofsky Performance Status

A Karnofsky performance status must be completed within 30 days before study entry.

Vital Signs

Temperature, pulse, and blood pressure collected at all visits and kept as a part of the source document.

6.3.7 Laboratory Evaluations

For all visits record all Grade ≥ 2 laboratory toxicities on the CRFs throughout the course of the study. All values, regardless of toxicity, of specific laboratories will also be recorded on the laboratory CRF; including: wbc, neutrophil count, hemoglobin, platelets, blood urea nitrogen, creatinine, glucose, AST/ALT, alkaline phosphatase, and total bilirubin.

Any laboratory toxicities that lead to a change in treatment, regardless of Grade, must be recorded on the adverse event CRF.

Refer to the Division of AIDS Table for Grading Adult Adverse Experiences, which can be found on the CCTG website: www.cctg.ucsd.edu

Hematology:

Hemoglobin, hematocrit, white blood cell count (WBC), differential WBC, absolute neutrophil count (ANC), and platelet count will be performed in real time at the site's local laboratory.

Blood volume: 3 mL

Coagulation tests

For subjects enrolled in the CSF Sub-Study: Prothrombin time, partial prothrombin time and calculation International Ratio (INR) will be performed in real time at the site's local laboratory.

Blood volume: 3 mL

Liver & Kidney Function Tests

Total bilirubin, AST (SGOT), ALT (SGPT), and alkaline phosphatase, BUN, creatinine, electrolytes (sodium, potassium, chloride, and bicarbonate) will be performed in real time at the site's local laboratory.

Blood volume: 7 mL

Pregnancy Test

For women with reproductive potential: Urine β -HCG (urine test must have a sensitivity of ≤ 50 mIU/mL) should be done at the site's local laboratory during screening, at study entry and whenever clinically suspected.

5 ml urine

6.3.8 Immunologic Studies

Nadir CD4+

The subject's prior nadir CD4+ cell count (absolute value and date) should be documented during screening and, when possible, a copy of the nadir CD4+ cell count report should be included in the source document. If this documentation is not available, then subject recollection will suffice. For subjects who do not know the exact nadir value and for whom there is no source documentation, then recall of the categorical nadir (e.g., <50 , <100 , <200 cells/mm³) will suffice.

CD4/CD8

A screening CD4/CD8 count and percentage must be performed at the site's local laboratory within 30 days prior to study entry unless a CD4 value is available from a CLIA-certified laboratory within 30 days of screening.

Because of the diurnal variation in CD4+ and CD8+ cell counts; all determinations should be obtained consistently in either the morning or the afternoon throughout the study, if possible.

Blood volume: 5 mL

Extended Flow Cytometry Markers

Extended flow markers for activation, maturation and regulatory function will be evaluated on CD4+/CD8+ T-cells. Samples will be collected at pre-entry, entry and on weeks 4 and 24. Pre-entry and entry laboratories must be separated by a minimum of 48 hours. These analyses will be done on fresh samples in real-time. **Specimens will need to be shipped ambient, overnight and in real-time to the UCSD central laboratory.**

Blood volume: 10 mL

6.3.9 Virologic Studies

Plasma HIV-1 RNA

A screening HIV-1 RNA must be performed at the site's local laboratory within 30 days prior to study entry unless a HIV-1 RNA value is available from a CLIA-certified laboratory within 30 days of screening.

Plasma HIV-1 RNA should be performed at the same local laboratory during the study and collected at entry, weeks 4, 24, 36 and in instances of virologic failure.

Genotype Resistance and Tropism Assay

Samples for genotypic and viral tropic analysis obtained at the time of virologic failure will be tested in real time for subject management by the site's local laboratory. All resistance testing results should be scanned and uploaded on the on-line data collection system for review by the protocol team (www.cfar.ucsd.edu/intranet). The study does not provide resistance testing.

Stored Plasma

Stored Plasma will be collected at pre-entry, study entry, and weeks 4, 24 and 36.

* Specimens will be stored at the site's local laboratory and batched shipped to the central laboratory (UCSD) after completion of the study.

Blood volume for combined HIV RNA and stored plasma: 15 mL

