- Consider baseline tropism testing.
- Avoid in patients with dual/mixed or CXCR4-tropic HIV-1 as antiviral efficacy was not demonstrated in a phase 2 study of this patient group.
- The safety and efficacy have not been established in treatment-naïve adult patients or pediatric patients. [*although trials of MVC in naïve patients have shown comparable (though not strictly non-inferior) virologic efficacy to and EFV-containing regimen in this population*]

The current study proposes to use MVC for treatment-experienced patients with on-going viral suppression and without evidence of multi-drug resistant virus. Since the patients will have undetectable HIV RNA levels, baseline tropism

testing is not possible. The use of MVC in this patient population should be safe and offers potential therapeutic benefit for the following reasons:

First, in phase 3 studies, treatment failure on MVC was associated with detection of CXCR4-using (i.e., CXCR4- or dual/mixed-tropic) [23]. This CXCR4-using HIV virus could have appeared in two ways: 1. due to *de novo* mutations in viral envelope or 2. due to emergence of pre-existing, low frequency variants that were not detected on baseline tropism testing. In both scenarios, as consistent with development of drug resistance with other HIV medications, MVC-associated drug resistance emerged in the setting of on-going HIV replication (i.e. detectable plasma HIV loads). An important difference in the treatment population of this study is that subjects would have already initiated ARV therapy and achieved viral suppression for at least 12 months prior to study enrollment. In the setting of on-going viral suppression it is very unlikely that CXCR4 tropic virus will be selected during the 24 weeks of MVC treatment intensification.

Second, the clinical and laboratory safety and tolerance of MVC is comparable to standard therapy in both treatment-experienced [26] and treatment-naïve patients [25]. Among treatment-naïve patients, the rate of discontinuation due to adverse events was less in the MVC arm (4.2%) than among efavirenz-treated subjects (13.6%) [25].

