6.1 Schedule of Events – Clinical Evaluations

	Screening	Pre-Entry	Entry	Maraviroc Therapy Intensification (24 weeks)					Post-Maraviroc Intensificatoin	Treatment Failure, Tox or Premature D/C
	Within 30 days of entry	> 48 hrs before entry	Day 0	Week 2	Week 4	Week 8	Week 12	Week 24	Week 36	
Informed Consent	X									
Medical/Medication History	X									
Documentation of HIV	X									
Clinical Assessment / AE			X	X	X	X	X	X	X	X
Documentation of within criteria HIV RNA and CD4 prior to screen labs	X									
Complete Physical Exam			X							X
Targeted Physical Exam							X	X	X	
Start and Dispense Drug			X		X		X			
Stop and Collect Drug								X		X
Concomitant Medications	X		X	X	X	X	X	X	X	X
Adherence Assessment	X		X	X	X	X	X	X	X	X

CCTG 590
Protocol version 1.0
August 13, 2008

Schedule of Events – Laboratory Evaluations

	Screening	Pre-Entry	Entry	Maraviroc Therapy Intensification (24 weeks)					Post-Maraviroc Intensification	Treatment Failure, Tox or Premature D/C
	Within 30 days of entry	> 48 hrs before entry	Day 0	Week 2 (± 1 wk)	Week 4 (± 1 wk)	Week 8 (± 2 wk)	Week 12 (± 2 wk)	Week 24 (± 2 wk)	Week 36 (± 2 wk)	
Hematology (local lab)	X		X	X	X	X	X	X	X	X
Prothrombin time (local lab) †	X									
Chemistry / LFT (local lab)	X				X		X	X	X	X
Pregnancy test (local lab)	X	And anytime when suspected								
CD4+/CD8+ (local lab)	X		X	X	X	X	X	X	X	X
§ CD4 ≤ 350; HIV RNA ≤ 50	X									
Plasma HIV-1 RNA PCR (local lab)	X		X		X			X	X	X
Plasma for MVC levels †			X		X			X		
Extended flow cytometry & PBMC collection (UCSD lab)		X	X		X			X		
Microarray - PBMCs collection (local processing in real-time)			X		X			X		
Lumbar puncture†			X		X			X		
Plasma for storage			X		X			X	X	
Serum for storage			X		X			X	X	
Ship ambient sample for extended flow in real-time		X	X		X			X		
Ship frozen all stored PBMCs, plasma and serum									X	
HIV Resistance & Tropism testing										X

§ If available within 30 days of screen then do not need to repeat laboratory test and can use value obtained within 90 days as screen value

† Only for subjects co-enrolled in the central nervous system sub-study

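### No plasma HIV RNA is scheduled between weeks 4 and 24 of maraviroc; one test at the existing week 12 visit would be a cheap improvement

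*Combined protocol and SAP*

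**What the plan says.** Section 6.3.9 gives the collection times for plasma HIV-1 RNA: "collected at entry, weeks 4, 24, 36 and in instances of virologic failure". In the laboratory table of section 6.1, the row beginning "Plasma HIV-1 RNA PCR (local lab" is marked at screening, entry, weeks 4, 24 and 36, and in the column for failure, toxicity or premature discontinuation. Weeks 2, 8 and 12 are blank. The two places agree.

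Section 6.2.7 leaves virologic failure on MVC to case-by-case judgement by the site investigator with the protocol team, and offers a working definition: "Suggested criteria include: two consecutive HIV RNA loads > 50 copies/mL". After a first value above 50 copies/mL, "a confirmatory plasma HIV-1 RNA test must be performed within 4 weeks of the initial HIV-1 RNA sample". On confirmed failure, "The patient will be followed off study medication but on study for the remainder of the study".

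Section 5.1.3 ends MVC at week 24 for every subject. Section 3.1 has visits on MVC at weeks 2, 4, 8, 12 and 24. Section 6.1 has hematology, chemistry and CD4/CD8 drawn at week 12, and study drug dispensed then for the last time before week 24.

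**The concern.** Section 6.2.7 is a participant-protection rule, and it can act only once an RNA test has shown a rebound. After week 4, the next scheduled test coincides with the planned end of MVC. The provision for sampling at virologic failure does not help, because the failure must already have been found. The confirmatory test likewise needs a first high value, and the discontinuation column needs a discontinuation.

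What is at stake is longer MVC use while virus is replicating. Section 2.3 says MVC resistance in the phase 3 studies emerged during ongoing replication, and tropism cannot be tested at entry because subjects are suppressed. The main argument there for proceeding is conditional on suppression: "In the setting of on-going viral suppression it is very unlikely that CXCR4 tropic virus will be selected during the 24 weeks". That condition goes without a scheduled check for 20 of the 24 MVC weeks.

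**Working it through.** The plan states no figure for detection delay, so there is nothing to reproduce. The check is arithmetic on the visit schedule.

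**Inputs from the documents.** RNA on MVC at weeks 4 and 24 (6.1, 6.3.9). Windows of 1 week at week 4 and 2 weeks at weeks 12 and 24 (6.2.2). MVC ends at week 24 (5.1.3). Confirmation within 4 weeks (6.2.7). 30 subjects (3.1).

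**Assumptions.** Rebound onset is uniform over weeks 4 to 24, rebound persists once begun, and there is no RNA testing outside the study. The lag L from first high sample to MVC stop is taken as 2, 4 or 6 weeks. It covers confirmation, result turnaround and the case-by-case decision.

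**Gap.** 24 − 4 = 20 weeks. With windows, the shortest is 22 − 5 = 17 and the longest is 26 − 3 = 23.

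**Share of rebounds with a scheduled RNA before MVC ends.**
- Current plan: 0/20 = 0%.
- With week 12: (12 − 4)/20 = 40%.

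**Mean wait from onset to next scheduled RNA** = sum of gap² / (2 × 20).
- Current plan: 20²/40 = 10.0 weeks.
- With week 12: (8² + 12²)/40 = 208/40 = 5.2 weeks. The longest gap falls from 20 to 12 weeks.
- With weeks 8 and 12: (4² + 4² + 12²)/40 = 176/40 = 4.4 weeks.

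**MVC exposure during rebound.** Under the current plan it runs from onset to week 24, mean 10.0 weeks. With a test at week v, the saving per rebound is (v − 4)/20 × (24 − v − L).

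| Lag L, weeks | Saving with v = 12 | Mean exposure left |
|---|---|---|
| 2 | 0.4 × 10 = 4.0 | 6.0 |
| 4 | 0.4 × 8 = 3.2 | 6.8 |
| 6 | 0.4 × 6 = 2.4 | 7.6 |

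The week 12 window matters little. At L = 4, a draw at week 10 gives 0.3 × 10 = 3.0 and a draw at week 14 gives 0.5 × 6 = 3.0.

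**Scale over the trial.** The documents give no rebound rate, so three are assumed. Planned MVC exposure is 30 × 24 = 720 weeks.

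| Assumed rate, weeks 4–24 | Expected rebounds of 30 | Found at week 12 (× 0.4) | MVC-weeks saved at L = 4 (× 3.2) | Share of 720 |
|---|---|---|---|---|
| 2% | 0.6 | 0.24 | 1.9 | 0.3% |
| 5% | 1.5 | 0.6 | 4.8 | 0.7% |
| 10% | 3.0 | 1.2 | 9.6 | 1.3% |

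**Interim review trigger (9.5).** It needs more than five events. The binomial probability that rebounds alone give 6 or more in 30 subjects is below 0.01% at a 2% rate, 0.3% at 5% and 7.3% at 10%.

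**The case against.** The best case for the plan as written has five parts.

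- **This is a choice, not an error.** Sections 6.1 and 6.3.9 are consistent, and nothing in the documents requires RNA more often. Eligibility (4.1.6) itself accepts as few as three values in 12 months as evidence of suppression. This stands, so the point is an improvement and not a correction.
- **Routine care may find rebounds.** Subjects are selected for having at least three RNA values in the past year, and their background regimen remains prescription care outside the study (5.3.1). The protocol does not say such testing continues, so it cannot be relied on. If it does continue, the waits and savings above are overstated.
- **The harm is not quantified.** Section 2.3 describes MVC as having direct antiviral activity, and the section on CD4 recovery (2.2.1.2) concludes that MVC is safe with CXCR4 or dual/mixed virus. Section 2.3 also cites comparable tolerability. Nothing in the documents converts weeks on MVC during rebound into a resistance or clinical risk. This limits the weight of the point, but the link between resistance and replication is the protocol's own.
- **Rebound should be uncommon.** Subjects are on an initial regimen with 12 months of suppression (isolated values below 1000 copies allowed) and report more than 90% adherence. Adherence and clinical checks continue at weeks 8 and 12, although they do not measure RNA. This stands.
- **The change is not free of extra visits.** No visit falls between weeks 12 and 24, so a week 12 value above 50 copies/mL needs an unscheduled confirmatory draw, even if it proves transient. This also stands.

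A reader might infer that the off-MVC rule can never act. The documents do not support that: a high week 4 value can be confirmed by about week 8 and acted on, and an unscheduled test could reveal a later rebound. A reader might also point to the absence of stored plasma at weeks 8 and 12 (6.3.9). That has no bearing here, because stored specimens are shipped in batch after the study and could not speed detection.

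**Conclusion.** The point holds as a cheap improvement of low severity. As scheduled, RNA testing cannot bring the off-MVC rule into play for any rebound starting after the week 4 sample. A week 12 test would make it available for 40% of such rebounds and save about 2.4 to 4.0 MVC-weeks per rebound, averaged over all onsets from week 4 to week 24. This rests on uniform onset, persistent rebound, no non-study RNA and a lag of 6 to 2 weeks. The 60% of rebounds starting in weeks 12 to 24 gain nothing. The total over 30 subjects is small at any of the assumed rates.

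A reader might go further and infer that the gap undermines the trial's results or its safety oversight. The documents do not support that. The primary endpoint is gene expression and is unaffected. The interim review trigger is unlikely to be reached by rebounds alone at the assumed rates, and the descriptive summary of virologic failure (9.4, secondary item 10) would lose little, since many transient episodes would not meet the two-value criterion.

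**What to change.** Mark plasma HIV-1 RNA at week 12 in the laboratory table of 6.1, and add week 12 to the collection times in 6.3.9, so that scheduled samples fall at entry and weeks 4, 12, 24 and 36, with the failure-driven sample kept. Leave 6.2.7 and 9.5 unchanged. State that weeks 12 to 24 remain without a scheduled test because no visit falls there.

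Costs:
- About 30 local-laboratory assays, drawn with blood already planned for week 12.
- At most 15 mL of blood per subject. That figure is an upper bound, since 6.3.9 gives it as "Blood volume for combined HIV RNA and stored plasma: 15 mL". It is 15/200 = 7.5% of the roughly 200 mL in 6.2.2 for weeks 2 to 24.
- An unscheduled confirmatory draw within 4 weeks for each week 12 value above 50 copies/mL, including transient blips. The documents give no basis for estimating how many.

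Testing at week 8 as well would cut the mean wait only from 5.2 to 4.4 weeks for about 30 further assays, so week 12 alone is the better value.

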6.3.10 Specimens for Serum Lipopolysaccharide (LPS) measurements

Stored Serum

Stored Serum will be collected at pre-entry, study entry, and weeks 4, 24 and 36.

* Specimens will be stored at the site's local laboratory and batched shipped to the central laboratory (UCSD) after completion of the study.

Blood volume: 10 mL

